7.7 Subject withdrawal Criteria

Subjects will be discontinued from the study for any of the following reasons:

- If the subject withdraws his or her consent for any reason.
- If the subject's condition has worsened to the degree that the investigator feels, it is unsafe for the subject to continue in the study.
- If the subject's drug code is unblinded.
- If an adverse event occurs for which the subject desires to discontinue treatment or the investigator determines that it is in the subject's best interest to be discontinued.
- If the subject with a score of ≥ 20 mm on a 0-100 mm Visual Analog Scale (VAS) for the contralateral knee
- If there is a significant protocol violation.
- If the subject is lost to follow-up. (The investigator will document all attempts to reach the subject by telephone and/or in person in source documents before considering that subject lost to follow-up.)
- If the female subject becomes pregnant.
- Treatment failure based on investigator's discretion.

- Administrative reasons.

The reasons for a subject being discontinued will be documented in the source notes and captured in case report form.

If a subject is discontinued from the study for any reason, the Day 28/ Early Termination Visit procedures should be completed and any outstanding data and study drug should be collected. Data, in addition to the reason for discontinuation and the date of removal, will be captured on the End of Study section of eCRF.

In the event that a subject discontinues from the study at any time due to an adverse event, the reason for discontinuation, the nature of the event and its clinical course must be fully documented. For such a subject, the investigator must strive to follow the subject until the adverse event has resolved, become clinically insignificant, is stabilized, or the subject is lost to follow-up.

Should a serious adverse event be noted, procedures stated in [Section 11.2.2](#) must be followed.

7.8 Premature Termination of Study in a Study Center

The Sponsor reserves the right to discontinue the study at any time. The reasons will be discussed with the Investigator. A study site may also be discontinued by the Sponsor for significant deviations from the protocol or due to difficulties experienced in running the study at that center.

The Sponsor may terminate this study in one particular or several study center(s) for one of the following reasons:

- Non-compliance with GCP and/or regulatory requirements
- Center cannot recruit an adequate number of patients
- False documentation in the eCRF due to carelessness or deliberately
- Inadequate co-operation with the Sponsor or its representatives
- The Investigator requests closure of his/her study center

If the study is prematurely terminated in one or more study centers, all Investigators have to inform their patients and take care of appropriate follow-up and further treatment of the patients. Ethics Committees and regulatory authorities will be informed about the reason and time of termination according to the applicable laws and regulations.

7.9 Termination of the Study

Premature termination of this study may occur because of a regulatory authority decision, change in opinion of the IRB/IEC, drug safety problems, or at the discretion of Mylan [REDACTED], [REDACTED]. In addition, Mylan [REDACTED] retains the right to discontinue development of generic formulation of diclofenac gel at any time.

If a study is prematurely terminated or discontinued, Mylan [REDACTED] will promptly notify the investigator. After notification, the investigator shall contact all participating subjects. As directed

by Mylan Laboratories Limited, all study materials must be collected and all CRFs completed to the greatest extent possible.

7.10 Treatment Compliance

A Subject Diary will be provided to all subjects where it is required to document the date and time of application of the medication. In the subject diary, subjects will also note of any adverse event observed, date and time of rescue medication administration and any concomitant medication taken or changed.

Compliance will be determined from the subject diary, which the subject will be trained and instructed to use to record all doses, as well as all missed doses. The number of missed and additional doses will be captured on the compliance page of the eCRF.

The used study medication tubes will be returned to the study site at appropriate visits or early termination or as applicable.

Subjects who are not compliant with application will be re-c counseled during the study visits.

Subjects who will take less than 75% (<84 applications) of total study drug during the study will be considered non-compliant and discontinued from the study. Subjects who will take more than 125% (>140 applications) of study drug are also considered non-compliant and the same subjects will not be considered for the Per-protocol (PP) population.

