10.3.2 Visit 4: Interim Visit (Week 2/Day 14 ± 4)

The following procedures will be performed.

- **Physical Examination and Vital signs**
- **Urine Pregnancy Test** (for all females of childbearing potential) if clinically indicated.
- **Subject diary review**
- **Assessment of treatment compliance**

- **Pain on Movement (POM) assessment in both the knees- 100mm VAS**
- **WOMAC pain score assessment of the target knee**
- **IMP dispensing**
- **Collection of the unused IPs**
- **Rescue medication dispensing (if required)**
- **Application site reaction assessment**
- **Assess Adverse Events**
- **Assessment of Concomitant Medications.**

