12.2.3 Per-Protocol Population (PP)

The per-protocol population (PP) includes

1. The per-protocol population will be the definitive population for equivalence analysis.

2. All randomized subjects who meet all the inclusion/exclusion criteria.
3. Completed study in compliance with the protocol.
4. Administered a pre-specified proportion of the scheduled doses (e.g., 75% to 125%) of the assigned product for the specified duration of the study.
5. Returned to the study site for the primary endpoint visit within the specified window (+/- 4 days) OR discontinued from the study as a treatment failure.
6. Subjects discontinued early from the study due to lack of treatment effect should be included in the PP population, using Last Observation Carried Forward (LOCF).

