12.3 Efficacy Analysis

1. The primary endpoint of the study is Mean change in the total WOMAC pain subscale score for the target knee, from baseline to week 4 in [Section 8.1](#) of this protocol.
2. All Efficacy analyses will be performed on the per-protocol and mITT populations. PP population will be definitive for equivalence analysis and mITT population will be definitive for superiority analysis.

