## **6.6 Per Protocol Population (PP Population)**

The Per Protocol (PP) population includes all mITT subjects who:

- met all inclusion/exclusion criteria
- apply 75% to 125% (both inclusive) of the scheduled applications of the assigned product
- return for the 4 week evaluation of WOMAC Pain Subscale score within the visit window (+/- 4 days; i.e., study Day 24-32) or discontinue from the study due to treatment failure (included as treatment failures)
- have no major protocol deviations impacting the primary efficacy outcome measure.

These major protocol deviations are described in [section 7.9](#). The list of protocol deviations which lead to exclusion of subjects from the PP population will be finalized at the Blind Data Review (BDR) meeting to be held prior to database lock.

This population will be used for testing the clinical equivalence.

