## 7.9 Protocol Deviations

Protocol deviations will be derived algorithmically and additionally reported by study centers according to the MYL-1601N-3002 Protocol Deviations Guidance Document. Eventually all approved protocol deviations will be entered in the Protocol Deviations eCRF page.

Subjects with protocol deviations deemed to have an impact on treatment evaluation will be excluded from the Per Protocol population. The list of protocol deviations which lead to exclusion of subjects from the PP population will be finalized at the Blind Data Review (BDR) meeting to be held prior to database lock.

Major deviations that have an impact on treatment evaluation may include:

- Violation of inclusion/exclusion criteria
- Use of prohibited medications
- Missing WOMAC Pain Subscale assessments
- Final visit out of window
- Missing visits
- Violation of rescue medication use rules
- IP compliance <75% or >125%
- Administration of incorrect or expired IP

Protocol deviations will be summarized by deviation category and treatment group. This analysis will be performed for all randomized subjects.

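### Protocol 7.10 withdraws gel under-users whom PP already excludes, so any withdrawn before Visit 5 enter mITT and ITT with a carried-forward Week 4 score

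*Protocol*

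**What the plan says.** Protocol 7.10 treats the two kinds of non-compliance differently. Subjects who take "less than 75% (<84 applications) of total study drug during the study will be considered non-compliant and discontinued from the study". Those above 125% (more than 140 applications) "are also considered non-compliant and the same subjects will not be considered for the Per-protocol (PP) population", and nothing is said about withdrawing them. The same section has non-compliant subjects re-counselled at visits and adds that "The number of missed and additional doses will be captured on the compliance page of the eCRF".

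The PP definitions already apply the limit. Protocol 12.2.3 requires that the subject "Administered a pre-specified proportion of the scheduled doses (e.g., 75% to 125%) of the assigned product for the specified duration of the study", and SAP 6.6 that the subject "apply 75% to 125% (both inclusive) of the scheduled applications of the assigned product". SAP 7.9 lists compliance below 75% or above 125% among the possible major deviations and says "Subjects with protocol deviations deemed to have an impact on treatment evaluation will be excluded from the Per Protocol population".

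On the roles of the populations, protocol 12.3 states: "PP population will be definitive for equivalence analysis and mITT population will be definitive for superiority analysis". SAP 7.11.2.1 also runs equivalence on mITT and ITT as sensitivity analyses.

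For anyone discontinued, protocol 7.7 calls for the Day 28/Early Termination procedures, which include the WOMAC; no later Week 4 visit is planned. SAP 6.5, 7.10 and 7.11.2 then bring early discontinuers into mITT (if eligible, with a post-baseline WOMAC) and into ITT by LOCF. SAP section 8 reports no changes from the protocol, so the withdrawal clause stands.

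**The concern.** Withdrawing an under-user protects no analysis. PP loses the subject either way, and mITT and ITT keep the subject either way. What can change is the value analysed in mITT and ITT: an observed Week 4 score if the subject stays, an older score carried forward if the subject is withdrawn before Visit 5.

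This matters because mITT decides both superiority tests, and the study succeeds only if both of those and equivalence are shown (SAP 7.1.2). Under-use may also be related to outcome: a subject may stop applying the gel because it does not help or because the pain has gone. Missing Week 4 data created in this way may therefore be informative, and here they would be created by the protocol itself.

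**Working it through.** **1. The plan's limits.** SAP 7.12.2 plans 112 applications (28 days, 4 a day). 0.75 × 112 = 84 and 1.25 × 112 = 140. Both figures in protocol 7.10 reproduce.

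**2. Who can be affected.** The limit applies to the total for the whole study. An under-user identified at Visit 5 has the Week 4 WOMAC taken at that visit and loses nothing. Between baseline and Week 4, the only visit with "Subject diary review" and a compliance assessment is Visit 4 (Day 14 ± 4). The telephone contact midway between Visits 4 and 5 also covers compliance, but without a diary review.

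**3. When 84 becomes unreachable.** At no more than 4 applications a day, the condition is: applications so far + 4 × days left ≤ 83.

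| Applications counted to | Dosing ends | Sum | Unreachable at or below |
|---|---|---|---|
| End of Day 14 | Day 28 | 27 + 56 = 83 | 27 of 56 |
| End of Day 18 | Day 28 | 43 + 40 = 83 | 43 of 72 |
| End of Day 13 (Visit 4 on Day 14) | Day 28 | 23 + 60 = 83 | 23 of 52 |
| End of Day 17 (Visit 4 on Day 18) | Day 28 | 39 + 44 = 83 | 39 of 68 |
| End of Day 14 | Day 32 | 11 + 72 = 83 | 11 of 56 |
| End of Day 18 | Day 32 | 27 + 56 = 83 | 27 of 72 |

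These are arithmetic limits, not protocol cut-offs and not projections at the subject's current rate. Additional or later applications, which protocol 7.10 and SAP 7.1.1 provide for recording, can still bring a subject back to 84.

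**4. How often that point is reached by Visit 4.** The documents give no adherence distribution. As an illustration, treat each application as independent with a fixed probability of being made (binomial).

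| Count and dosing end | 50% adherence | 60% | 70% |
|---|---|---|---|
| 27 of 56, Day 28 | 45% | 4.9% | 0.05% |
| 43 of 72, Day 28 | 96% | 53% | 4.1% |
| 23 of 52, Day 28 | 24% | 1.5% | 0.01% |
| 39 of 68, Day 28 | 91% | 37% | 1.8% |
| 11 of 56, Day 32 | about 0% | about 0% | about 0% |
| 27 of 72, Day 32 | 2.2% | 0.01% | about 0% |

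So early certainty is possible for severe under-use with dosing to Day 28, more so when Visit 4 is late, and is rare if dosing can run to Day 32.

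**5. Age of the carried score.** For withdrawal at Visit 4: nominally 28 − 14 = 14 days before Week 4. With both visit windows, the minimum is 24 − 18 = 6 days and the maximum 32 − 10 = 22 days.

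**6. Size, under assumptions.** The planned active–placebo difference is 5.85 − 4.68 = 1.17 points, with SDs 4.23 and 4.89 (SAP 3.2) and 363 per arm (SAP 3.2.2). SE = √((4.23² + 4.89²)/363) = 0.339.

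Three inputs are assumed because the documents give none of them:
- under-users: 3% to 5% (12 to 20 of 404 per arm);
- share of these withdrawn before Visit 5: 10% to 50% (about 1 to 10 per arm);
- between-arm difference in carry-forward error: 0.5 to 1.17 points.

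Bias = under-use share × share withdrawn early × between-arm error.
- Low: 0.03 × 0.10 × 0.5 = 0.0015 points; 0.0015/1.17 = 0.1%; 0.0015/0.339 = 0.004 SE.
- High: 0.05 × 0.50 × 1.17 = 0.029 points; 0.029/1.17 = 2.5%; 0.029/0.339 = 0.09 SE.

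This illustration uses the same withdrawal share in both arms. It is neither a bound nor an estimate.

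**The case against.** The strongest reply is that the text does not prescribe the harmful event. The limit is a total over the study, SAP 7.12.2 divides actual applications by 112, protocol 7.10 answers non-compliance seen at visits with re-counselling, and the withdrawal list in 7.7 does not name non-compliance. On that reading the total is settled at Visit 5, where the WOMAC is taken anyway. This largely stands. A reader might infer that 7.10 orders withdrawal at Visit 4, or that under-users as a group lose their Week 4 score; the documents support neither. What remains is that 7.10 states discontinuation outright and sets no interim rule, so a site may act early. If no site does, the clause serves no purpose.

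Second, some data are kept: the early termination procedures include a WOMAC, so the carried value should be an on-study score from about the time of withdrawal. That is true, but it is still not a Week 4 score.

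Third, there may be a patient-interest reason to release someone who barely uses the gel while NSAIDs and opioids are prohibited (protocol 7.13). The documents do not give this reason, and withdrawal for safety or consent would remain available.

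Fourth, the effect is tiny on any plausible input. That stands and sets the priority.

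**Conclusion.** The point holds as a minor one. The discontinuation clause gives PP no protection that it does not already have, and it can replace an observed Week 4 score by a carried-forward one in mITT and ITT for under-users withdrawn before Visit 5. How many that would be, and in which direction the result would move, cannot be determined from the documents. The illustrative 0.004 to 0.09 SE rests wholly on assumed rates of under-use and early withdrawal and an assumed carry-forward error; its upper end needs half of all under-users withdrawn early and a between-arm error as large as the whole planned effect.

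A reader might go on to infer that the superiority tests are at risk or that the equivalence conclusion is biased. The documents do not support this: the primary equivalence analysis uses PP, which excludes these subjects whether or not they are withdrawn, and the sample size does not change. The confidence that the clause acts in practice is only moderate, since it depends on how sites read a whole-study limit.

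**What to change.** In protocol 7.10, replace the discontinuation wording for under-users with the consequence already stated for over-users, namely exclusion from PP. Add that the subject is re-counselled, stays in the study, and has the Visit 5 WOMAC and VAS in the Day 24–32 window unless safety or consent requires withdrawal, and that the observed Week 4 score is used in mITT and ITT.

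In protocol 7.7, add that low gel compliance alone is not a significant protocol violation requiring withdrawal. Without this, the same subject could still be withdrawn on that ground, because SAP 7.9 lists compliance below 75% as a possible major deviation.

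Cost: a short amendment with sponsor and IEC/IRB approval, and prior regulatory approval if it is judged substantial (protocol 14.6). Visit 5 is already scheduled, and the PP definition and sample size stay as they are. The downside is that some Week 4 scores from subjects with low exposure enter mITT; those eligible with a post-baseline WOMAC would be in mITT anyway, with an older score. The change is worth including in an amendment made for other reasons.

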7.11 Study Medication Accountability

When a drug shipment is received at a study center, the investigator/designee shall sign the receipt form provided with the shipment.

Subjects shall be instructed to return used, partially used, or unused study medication kits to the study center staff so that any remaining drug supplies can be accounted for and noted in the log for accountability.

7.12 Return of Clinical Supplies

All used and unused kits of study medication will be handled as per Sponsor's instructions in IP handling plan after completion of the study.

7.13 Concomitant/Prohibited Treatment:

Any medication other than study drug, either prescription drug or OTC drug will be treated as concomitant medication.

All medications taken on a regular basis should be recorded in source data.

If drug therapy other than that specified in the protocol is required, it should be documented and have to be pre-approved by the investigator (if required in consultation with medical monitor/sponsor) prior to the subjects usage. Further, the Investigator (if required in consultation with medical

monitor/sponsor) decide the course of action for that participant based on the time the medication was administered and its pharmacology.

The following are **prohibited** during this study:

1. Any other topical or intraarticular products applied to the target site.
2. ACE-inhibitors, anticoagulants, cyclosporine, diuretics, lithium, methotrexate or oral NSAIDs.
3. Muscle relaxants
4. Sedative/hypnotics (stable dose for at least 14 days prior to baseline visit will be allowed)
5. Chondroitin/glucosamine
6. Opioids
7. Glucosamine
8. Chondroitin
9. Use occlusive bandages, ultrasound, transcutaneous electrical stimulation or any alternative therapies such as acupuncture, homeopathy or mesotherapy
10. Systemic corticosteroids or immunosuppressive drugs.
11. Pain medication other than acetaminophen (paracetamol) including topical NSAIDs
12. Non-pharmacological devices for knee pain like knee brace, herbal remedies.

Physical therapy will be permitted if this started at least 1 month before screening but cannot be initiated or changed during the study. Exercise regimens and the application of heat or cold will not be started, discontinued, or changed during the study.

Permitted Medications

Subjects will be allowed to continue taking stable (non-analgesic) medications that would not interfere with the metabolism of diclofenac.

Concomitant use of acetylsalicylic acid for cardiac prophylaxis with maximum 162 mg daily will be allowed during the study if the therapy is stable for at least 3 months.

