Study Rationale	
Mylan is developing a generic diclofenac sodium gel to the Reference Listed Drug (RLD) Voltaren® gel. This randomized, double-blind, three-arm, placebo controlled, bioequivalence study with clinical endpoint has been designed to establish clinical equivalence and safety of Mylan's diclofenac gel in the symptomatic treatment of osteoarthritis of knee compared to Voltaren® gel and to establish superiority in efficacy of both compared to a placebo (vehicle) gel.
 
The planned study design is also in compliance with the United States Food and Drug Administration's Draft Guidance for Diclofenac Sodium Topical Gel.¹

Dose and Mode of Administration	All subjects will have to apply 4 gm of gel to the affected area of target knee 4 times daily. At the start of run-in period, placebo gel will be provided to the qualified subjects for application and during the treatment period, Mylan's Diclofenac Sodium Topical Gel 1%, Voltaren® Gel 1% (Reference Listed Drug), or Placebo gel will be provided to the subjects for application. The proper amount of gel will be measured using the dosing card. The gel will be applied within the rectangular area of the dosing card up to 4-gram line. Subjects will be instructed to rinse and dry the dosing card after use. Subjects will be trained via a detailed and translated instruction subject diary on how to administer the study drug.
Study Population	Male or non-pregnant female aged \geq 35 years with a clinical diagnosis of osteoarthritis of the knee according to the American College of Rheumatology (ACR) criteria
Number of Subjects	Around 1212 patients will be randomized in this study (404 patients in each treatment arm).
Study Period	Total study duration for the clinical part will be around 56 days that includes screening period of 28 days (including run-in period of 7 (+ 4) days) and treatment period of 4 weeks.
Inclusion Criteria:	
 1. Healthy male or non-pregnant female aged \geq 35 years with a clinical diagnosis of OA of the knee according to the American College of Rheumatology (ACR) criteria² i.e. Knee pain along with at least 3 of the following 6 criteria 
 a. Age $>$ 50 years

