Cmax = maximum plasma concentration, tmax=time of Cmax. AUC₀₋₂₄=area under the concentration time curve. SD=standard deviation. CI=confidence interval.

The pharmacokinetics of VOLTAREN® GEL has been tested under conditions of moderate heat (application of a heat patch for 15 minutes prior to gel application) and of moderate exercise (first gel application followed by a 20-minute treadmill exercise). No clinically relevant differences of systemic absorption and of tolerability were found between applications of VOLTAREN® GEL (4 x 4 g per day on 1 knee) with and under the conditions tested. However, the pharmacokinetics of VOLTAREN® GEL were not tested under the condition of heat application following gel application. Therefore, concurrent use of VOLTAREN® GEL and heat is not recommended.

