4.1. Study Overview

This is a double-blind, multiple-site, randomized, parallel-design study to investigate the bioequivalence with clinical endpoint of Mylan's Diclofenac Sodium Topical Gel, 1% to Voltaren® Gel, 1% (Novartis US) and to investigate that both the active products are superior to placebo.

Subjects will have to visit the clinic for the following visits during the study –

[figure not shown]
Visit 1 – Screening visit (within 28 days prior to randomization)

Visit 2 – Start of Placebo Run-in period (Day -11 to Day -7)

Visit 3 – Randomization (baseline) visit (Day 0)

Visit 4 – Interim visit (Week 2/Day 14 ± 4)

Visit 5 – End of study (Week 4/Day 28 ± 4)/ Early termination visit

Figure 1: Study Design Flow Chart

WOMAC - Western Ontario and McMaster Universities Arthritis Index, POM - Pain on Movement

* Telephonic contact in midway for well-being, concomitant medication and treatment compliance

** Telephonic contact to stop usage of rescue medication for 3 days prior to clinic visit

After informed consent process and completion of all screening assessments, the eligible subjects will be requested to stop the currently ongoing osteoarthritis drug therapy. The wash out period (run-in period) of 7 days or \geq 5 half-life of previous osteoarthritis drug therapy, whichever is longer, will be maintained before the baseline visit. Subjects will undergo at least 7 days of placebo run-in period. In case subject extends run-in period beyond 11 days, continuation of the subject will be decided in consultation with Medical monitor.

The Pain on Movement (POM) score on a Visual Analog Scale (VAS) and Western Ontario and McMaster Universities Osteoarthritis Index (WOMAC Likert version 3.1) pain score will be recorded at the start of run-in Period and at the end of run-in Period (i.e. immediately prior to randomization on the day of baseline visit). Recording of the VAS will be done for both the knees and recording of the WOMAC pain score will be done for the target knee.

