10.2 Visit 2: Start of Placebo Run-in Period (Day -11 to Day -7)

- **Discontinuation of current osteoarthritis therapy**
- **Vital Signs**
- **Inclusion/Exclusion Criteria Review**
- **Urine Pregnancy Test** (for all females of childbearing potential) if clinically indicated
- **Pain on Movement (POM) assessment in both the knees- 100mm VAS**
- **WOMAC pain score assessment of the target knee**
- **Study Medication and Subject Diary Dispensing for Run-in Period:** Placebo gel for run-in period will be dispensed by the site staff to qualified subjects. A subject diary, containing instructions for subjects, will be dispensed to each qualified subject. First administration of gel will be supervised at the study center.
- **Instructions on placebo application and storage**
- **First placebo gel application at the site**

- **Assess Adverse Events**
- **Assessment of Concomitant Medications.**

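### Section 7.13 freezes heat use without excepting the target knee, although section 2.3 advises against combining the gel with heat (minor, precautionary)

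*Protocol*

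**What the plan says.** Section 7.13 (Concomitant/Prohibited Treatment) closes its list of prohibited treatments with a stability rule: "Exercise regimens and the application of heat or cold will not be started, discontinued, or changed during the study". The rule names no body site.

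Section 2.3 (Reference Product Information) reports two things about heat. A heat patch worn for 15 minutes before the gel was tested: "No clinically relevant differences of systemic absorption and of tolerability were found between applications of VOLTAREN® GEL" with and without it. For the reverse order, the pharmacokinetics "were not tested under the condition of heat application following gel application", and the section therefore concludes that "concurrent use of VOLTAREN® GEL and heat is not recommended".

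Two other lines might seem to bear on the question. Item 12 of the prohibited list in 7.13 reads "Non-pharmacological devices for knee pain like knee brace, herbal remedies". The Visit 2 procedures in section 10.2 include "Discontinuation of current osteoarthritis therapy".

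**The concern.** Section 7.13 is the rule that sites act on, while section 2.3 is background. For a subject who arrives already using heat on the target knee, the rule forbids stopping. The background section advises against having heat and gel together. The protocol thus tells such a subject not to follow a precaution that it records itself.

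What is at stake is a small safety inconsistency and an unclear instruction to sites. It is not the validity of the comparison.

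**Working it through.** No power, alpha or margin calculation is involved. The check is a reading of the provisions side by side, plus two day counts.

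**1. The two texts together.** Section 7.13 forbids discontinuing heat and does not except the target knee. Section 2.3 advises against heat with the gel. Sections 4.1 and 7.6 put the gel on the target knee four times daily. For a prior user of target-knee heat, following 7.13 to the letter means heat continues on gel-treated skin.

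**2. Does another visible provision resolve this?**

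- *7.13, item 1* bars other topical or intra-articular products at the target site. It could reach a heat rub, but it does not name heat.
- *7.13, item 9* bars occlusive bandages, ultrasound, electrical stimulation and alternative therapies. It does not name heat.
- *7.13, item 12* bars non-drug devices for knee pain. A heating pad could fit, because the knee brace is given only as an example. But heat is not named, and the sentence that does name heat comes later in the same section and forbids stopping it.
- *10.2, Visit 2* lists stopping current osteoarthritis therapy. The synopsis, protocol section 4.1 and SAP section 3.1 all describe this step as stopping osteoarthritis drug therapy, with a washout counted in half-lives. It does not cover heat.
- *Eligibility criteria (5.1, 5.2) and contraindications (2.5)* do not mention heat.
- *7.6 and the diary.* Part of 7.6 is redacted after the method of application, and the diary instructions are not supplied. A heat instruction may be there and is not counted as missing. If it tells subjects to avoid heat on the knee, it would still disagree with 7.13 as worded.

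No visible provision settles the matter.

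**3. How long heat and active gel could overlap.** The run-in gel is placebo, and randomized gel starts on Day 1. Visit 5 is Day 28 ± 4:

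- shortest: Day 1 to Day 28 − 4 = Day 24, about 24 days;
- longest: Day 1 to Day 28 + 4 = Day 32, about 32 days.

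This applies to the test and reference arms only. The 404 placebo subjects receive no diclofenac gel.

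**4. How many subjects.** The documents give no figure for heat use on the target knee, and none is assumed.

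**5. Length of the restriction under the proposed fix (Visit 2 to Visit 5).** Visit 2 is Day −11 to Day −7:

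- shortest: 7 + 24 = 31 days;
- nominal: 7 + 28 = 35 days;
- longest in the standard windows: 11 + 32 = 43 days.

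It can be longer if the run-in is extended: "In case subject extends run-in period beyond 11 days, continuation of the subject will be decided in consultation with Medical monitor". Visit 5 rescheduling after rescue use is not counted.

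**The case against.** The strongest reply is that the two texts are not rival instructions. Section 2.3 summarises product labelling. It says that heat is not recommended and does not forbid it, and heat is not among the contraindications. The 7.13 sentence is meant to hold co-interventions constant, and it orders nobody to heat gel-treated skin. Item 12 can be read to remove heating devices for knee pain, which would leave the stability rule to govern only what is still permitted. The redacted text in 7.6 may already carry the precaution.

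Much of this stands. It makes the point an ambiguity with a literal conflict inside it, and it keeps the weight low. It does not remove the point: no visible item names heat, and the one sentence that does forbids stopping it. Holding co-interventions constant is a sound aim, and the fix preserves it.

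A reader might infer three stronger things that the documents do not support:

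- *That the Visit 2 discontinuation step collides with 7.13.* It does not, because that step concerns drug therapy.
- *That subjects combine heat with active gel from Visit 2 onward.* They do not, because the run-in gel is placebo.
- *That harm has been shown.* Heat before the gel made no relevant difference, heat after it was simply not tested, and Table 1 puts systemic exposure at 4 x 4 g per day at 5.8% of oral.

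**Conclusion.** The point holds as a minor, precautionary inconsistency of low severity. Read literally, 7.13 keeps a prior user of target-knee heat on heat while active gel is applied, for about 24 to 32 days in the two active arms. The number affected is unknown and possibly zero.

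The conclusion rests on reading 7.13 as written and on the visible text only. It also takes the precaution, which section 2.3 states for the reference product, to be sensible for the test gel, for which the visible text gives no heat data.

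A reader might go on to infer bias in the Test/Reference ratio, in the placebo comparisons or in the per-protocol set. Nothing in the documents shows such an effect, and none is claimed.

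**What to change.** In section 7.13, prohibit heat on the target knee from the start of the placebo run-in (Visit 2) through Visit 5. Limit the no-change sentence to exercise, cold, and heat at other body sites. Add target-knee heat to the Visit 2 instructions in section 10.2. Check that section 7.6 and the diary agree.

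The edits belong together. The synopsis counts screening and run-in within the study ("Total study duration for the clinical part will be around 56 days that includes screening period of 28 days"), so a new Visit 2 stop would contradict the no-change sentence unless that sentence is narrowed.

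Starting at Visit 2 means that baseline, Week 2 and Week 4 scores are all taken without target-knee heat. Applying the rule to every subject keeps the blind.

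The cost is wording only, with no added visits, procedures or subjects. The burden falls on users, who give up target-knee heat for about five weeks (31 to 43 days in the standard windows). That includes heat before the gel, which section 2.3 found unproblematic, and heat during the placebo run-in.
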